9.4 Sample Size Considerations

Rev. Add1

OS will be estimated based on the KM method and compared between arms using the stratified log-rank test. All survival estimates are from randomization, which would be ~18 months from start of initial therapy. Median OS for the control arm was estimated to be 5.5 years (y) considering expectations in this setting for an unselected cohort as well as results from the previously mentioned meta-analysis according to post-treatment MRD status.³ Based on the log-rank test, there is approximately 80% power at 1-sided 2.5% significance to detect a difference in 4y OS from 60.4% to 72.2% reflecting an approximate 35% reduction in hazard [treatment HR=0.65] assuming 510 patients uniformly accrued over 3.5y and 179 deaths at full information (6y).

9.5 Projected Accrual

This study aims to screen 840 patients to pre-registration Step 0 at an accrual rate of 20 patients per month/240 patients per year for an accrual duration of 3.5y. With an allowance of 15% for patients not yielding high quality specimens for MRD analysis, it is expected that 714 patients will have MRD measured. MRD status is anticipated to be split 75% positive/25% negative resulting in 536 MRD positive patients and 178 MRD negative patients. Some drop-out (5%) between marker evaluation and enrollment to Step 1 treatment is also anticipated resulting in an estimated 510 patients randomized to Arm A or Arm B with 1:1 allocation. Patients with MRD negative disease status based on NGF and immunofixation results will not be registered to the treatment phase.

Rev. Add3

9.6 Randomization Scheme

Patients are randomized in equal allocation to ixazomib-lenalidomide or placebo-lenalidomide and stratified by molecular risk status by International Myeloma Working Group (IMWG) criteria: standard or high risk, prior lenalidomide maintenance dose: 5 mg, 10 mg, or >10 mg, prior maintenance duration: < 12 months or ≥ 12 months. Treatment will be assigned using permuted blocks within strata with dynamic balancing by main ECOG-ACRIN institution.³³

9.7 Gender and Ethnicity

Based on observed data from E1A11 the anticipated accrual in subgroups defined by gender and race is expected to parallel the newly diagnosed setting as follows:

Rev. Add3

DOMESTIC PLANNED ENROLLMENT REPORT (TREATMENT)					
Racial Categories	Ethnic Categories				Total
	Not Hispanic or Latino		Hispanic or Latino		
	Female	Male	Female	Male	
American Indian/ Alaska Native	2	4	0	0	6
Asian	6	4	0	0	10
Native Hawaiian or Other Pacific Islander	2	0	0	0	2
Black or African American	27	29	0	0	56
White	147	255	17	17	437
More Than One Race	0	0	0	0	0
Total	184	292	17	17	510

The accrual targets in individual cells are not large enough for definitive treatment comparisons to be made within these subgroups. Therefore, overall accrual to the study will not be extended to meet individual subgroup accrual targets.

Study Monitoring

This study will be monitored by the ECOG-ACRIN Data Safety Monitoring Committee (DSMC). The DSMC meets twice each year. For each meeting, all monitored studies are reviewed for safety and progress toward completion. When appropriate, the DSMC will also review interim analyses of outcome data. Copies of the toxicity reports prepared for the DSMC meetings are included in the study reports prepared for the ECOG-ACRIN group meeting (except that for double blind studies, the DSMC may review unblinded toxicity data, while only pooled or blinded data will be made public). These group meeting reports are made available to the local investigators, who may provide them to their IRBs. Only the study statistician and the DSMC members will have access to interim analyses of outcome data. Prior to completion of this study, any use of outcome data will require approval of the DSMC. Any DSMC recommendations for changes to this study will be circulated to the local investigators in the form of addenda to this protocol document. A complete copy of the ECOG-ACRIN DSMC Policy can be obtained from the ECOG-ACRIN Operations Office – Boston.

10. Specimen Submissions

Following pre-registration (Step 0), diagnostic bone marrow aspirates must be submitted to Mayo Clinic Hematology Laboratory for the central Minimal Residual Disease (MRD) assessment as described in Sections [1.1](#) and [11](#). The institution will be notified of the results within three (3) business days of receipt of the bone marrow specimen.

All specimens must be clearly labeled with the ECOG-ACRIN protocol number (EAA171), the patient's initials (last name, first name) and ECOG-ACRIN patient sequence number, the collection date, and specimen type.

It is required that all specimens submitted on this trial be entered and tracked via the ECOG-ACRIN Sample Tracking System (STS) [Section [10.3](#)]. An STS shipping manifest form is to be included with every submission.

Rev. Add1

10.1 Submissions to the Mayo Clinic Myeloma Reference Laboratory

Myeloma Tumor Biology Kits are available to order and will include materials necessary for the preparation and shipment of the specimens. To order kits contact [name] at the Mayo Clinic Myeloma Reference Laboratory at [contact] or email [contact]. Include the name of the contact person, phone number, address where kits should be shipped, ECOG-ACRIN protocol number (EAA171), the number of kits needed, and if the kits need to be shipped priority overnight. Otherwise kits will arrive in three to four working days.

Any questions concerning specimen collection and shipment can be directed to [name] at [contact] or [contact].

10.1.1 Sample Submission Schedule

Bone marrow specimens are to be submitted as indicated below:

Biological Materials ¹	Following Pre-registration
MANDATORY for Minimal Residual Disease Assessment	
Bone Marrow Aspirate (1) 6mL ACD (yellow top) tube	X

1. Kits are being provided for the collection and shipment of the bone marrow specimens.

10.1.2 Sample Preparation Guidelines

Bone Marrow Aspirate

This redirect bone marrow aspirate should be drawn at the same time that the bone marrow aspiration/biopsy is being done for clinical and diagnostic purposes and should be done through the same skin puncture site that the clinical specimen was obtained.

- Draw 6mL of "redirect" bone marrow aspirate into **one (1) ACD (yellow top) vacutainer tube** provided in the Myeloma Tumor Biology Kit. Please use the first or second pull for these tubes. Ship the day of collection.

10.1.3 Shipping Procedures

If your shipment was not logged into the ECOG-ACRIN STS, please call [name] at [contact] or email [contact] to notify the laboratory when specimens are being shipped. Indicate the ECOG-ACRIN protocol number (EAA171), the FedEx tracking number, and name and phone number of the contact person.

Bone marrow aspirates should be sent fresh, the day of collection, at ambient temperature (do not freeze) and shipped overnight to arrive during normal working hours. Specimens from multiple patients may be shipped together, but must be placed in separately labeled tubes and bags.

Follow the packing guidelines listed in the kit. If specimens are sent late in the week and will arrive on the weekend, please note "Saturday Delivery" on the Federal Express form.

FRIDAY AND PREHOLIDAY SHIPMENTS SHOULD BE AVOIDED.

Packing instructions:

- Place the slightly thawed Kool-PAK in the bottom of Styrofoam container (Kool-PAK should be frozen at least 24 hours in advance). Allow the frozen ice pack to thaw at room temperature for 2-3 hours before preparing the specimens for shipment.
- Place absorbent toweling on top of the Kool-PAK.
- Place specimens in their individual plastic bags provided, wrap in paper toweling and place them in the Styrofoam container and close the lid. Do not place the specimens directly on the ice pack.
- Place the Styrofoam container and the Sample Tracking System Shipping Manifest Form within the cardboard mailing sleeve.
- Prepare the package for shipping, applying packing tape as needed. Complete the sender portion of the return FedEx air bill and adhere to the exterior lid of the box. Ship specimens via priority overnight delivery the same day collected.
- Notify Federal Express for pick-up and/or leave package at the designated FedEx drop-off location.

The specimens in prepared kits should be shipped to the following address:

[name]
Mayo Foundation
[name]
[name]
[name]

An STS shipping manifest form must be generated and shipped with all specimen submissions.

10.2 Use of Specimens in Research

Specimens will be distributed to investigators at Mayo Clinic Hematology Laboratory for the laboratory research studies defined in Section [11](#).

Specimens from patients who consented to allow their specimens to be used for future approved research studies will be retained in an ECOG-ACRIN designated central repository.

Specimens submitted will be processed to maximize their utility for current and future research projects.

If future use is denied or withdrawn by the patient, the specimens will be removed from consideration for use in any future research study. Specimens will be destroyed per guidelines of the respective repository.

10.3 ECOG-ACRIN Sample Tracking System

It is **required** (barring special circumstances) that all specimens submitted on this trial be entered and tracked using the ECOG-ACRIN Sample Tracking System (STS). As of June 2007, the software will allow the use of either 1) an ECOG-ACRIN user-name and password previously assigned (for those already using STS), or 2) a CTSU username and password.

When you are ready to log the collection and/or shipment of the specimens required for this study, please access the Sample Tracking System software by clicking <https://webapps.ecog.org/Tst>.

Important: Please note that the STS software creates pop-up windows, so you will need to enable pop-ups within your web browser while using the software. A user manual and interactive demo are available by clicking this link: <http://www.ecog.org/general/stsinfo.html>. Please take a moment to familiarize yourself with the software prior to using the system.

An STS generated shipping manifest must be generated and shipped with all specimen submissions.

Please direct your questions or comments pertaining to the STS to [contact].

Study Specific Notes

Generic Specimen Submission Form (#2981v3), along with the Mayo Clinic Patient Information Form ([Appendix VII](#)), will be required only if STS is unavailable at time of specimen submissions. Notify the laboratory of the shipment by faxing a copy of the completed form to the laboratory.

Retroactively enter all specimen collection and shipping information when STS is available.

10.4 Sample Inventory Submission Guidelines

Inventories of all specimens submitted from institutions will be tracked via the ECOG-ACRIN STS and receipt and usability verified by the receiving laboratory. Inventories of specimens forwarded and utilized for the approved laboratory research studies will be submitted by the laboratory to the ECOG-ACRIN Operations Office - Boston on a monthly basis in an electronic format defined by the ECOG-ACRIN Operations Office - Boston.

11. Laboratory Research Studies

These analyses will be performed at the Hematology Laboratory at Mayo Clinic Rochester, MN under the direction of [name].

11.1 Assessment of Minimal Residual Disease

11.1.1 MRD – Next Generation Flow Cytometry Methods

Next generation flow cytometry (NGF) MRD assessment is conducted with multiparameter flowcytometry. The reagents for the MRD assessment will utilize the MM MRD kit (cytognos # MM-MRD, Salamanca). Analysis will follow the Euroflow approach using Infinicyt software as outlined by Flores-Montero et al.²² The methodology has been described before and will be used without additional modification. Briefly, it utilizes an 8-color flow approach using two tubes, one with cytoplasmic light chains assessment on permeabilized cells. Four milliliters (ml) BM aspirate will be lysed using a fixative free erythrocyte lysing solution (# CYT-BL (10X), Cytognos, Salamanca, Spain). Per manufacturers guidelines, up to two ml of marrow will be suspended in 50 ml of freshly made 1X lyse and gently mixed for 15 minutes. After centrifugation, the supernant is aspirated and the pellet resuspended in 2 ml of Staining Buffer (SB - PBS /0.09% Azide /0.5% BSA). The tube is then filled to 50 ml with staining buffer and centrifuged. Two ml of SB are used to resuspend one pellet and combined with the pellet in the second tube. The cell suspension is transferred to a 12 X 75 tube. After centrifugation, the supernant is aspirated and the pellet is resuspended in 0.5 ml of SB. The suspension is diluted with SB not to exceed 10⁷ per ml. Up to 10 million cells are added to tube 1 and tube 2. Both tubes are stained for 30 minutes at room temperature, in the dark with multi epitope CD38 FITC/CD138 V450/CD45 Percp 5.5 /CD19 PE-Cy7 in both tubes for plasma cell (PC) gating. To determine PC phenotype both tube 1 and 2 contain CD27-BV510 and CD56-PE; tube 1 also includes CD117 APC and CD81 APC C750. After incubation, tube 1 is resuspended for 10 minutes in BD FACs Lyse. The pellet is resuspended in 0.5 ml SB and held until run on the flow cytometer. Tube 2 is further processed for cytoplasmic light chain staining (Kappa APC /Lambda APC-C750) with a fix and perm step. After centrifugation, the pellet is resuspended in 0.5 ml SB and held until run on the flow cytometer. The bone marrow quality will be determined by assessing for expected normal marrow cells. Normal and neoplastic plasma cells will be reported as percentage of all CD38/138/45 gated cells. The report will include the total number of cells analyzed, PC immunophenotype (including clonality), and plasma cell (normal and abnormal) percentages and event (abnormal plasma cell) count to determine MRD negative or positive status.

11.2 Lab Data Transfer Guidelines

The data collected on the above-mentioned laboratory research studies will be submitted electronically using a secured data transfer to the ECOG-ACRIN

Operations Office - Boston by the investigating laboratories on a quarterly basis or per joint agreement between ECOG-ACRIN and the Investigator.

12. Imaging Correlative Studies

12.1 ¹⁸Fluorodeoxyglucose (FDG) PET/CT

Advanced imaging modalities are playing an increasingly important role in the diagnosis, risk stratification and response assessment of myeloma. ¹⁸F-FDG PET/CT allows simultaneous assessment of the bone marrow, as well as presence of extramedullary lesions. Both baseline assessments as well as follow up imaging have an important prognostic role and appear to be associated with survival. Myeloma cells, while they tend to be primarily marrow based, can be found in the extramedullary compartment, including the peripheral blood. As a result, imaging plays an important role in assessing response to therapy, as well as in identifying disease progression, both inside and outside the bone marrow. In fact, functional imaging assessment using ¹⁸F-FDG PET/CT is an integral part of minimal residual disease assessment in myeloma, in addition to following foci of extramedullary disease identified prior to start of treatment.

Rev. Add3

12.1.1 Imaging Schedule

All registered patients from both the ixazomib/lenalidomide arm and the placebo/lenalidomide arm are expected to undergo ¹⁸F-FDG PET/CT as SOC at the following time points:

- Prior to initiation of randomized study mandated therapy [referred to as the baseline scan]. The baseline scan can be done prior to study registration, as long as it is within 8 weeks of pre-registration step 0
- After completion of 12 cycles of study mandated therapy (\pm 6 weeks) [referred to as the year 1 scan]
- After completion of 24 cycles of study mandated therapy (\pm 6 weeks) [referred to as the year 2 scan]

All ¹⁸F-FDG PET/CT images are to be submitted via TRIAD as outlined in Section [4.3.5](#).

12.1.2 Criteria for defining abnormal ¹⁸F-FDG PET/CT

The primary ¹⁸F-FDG PET/CT reading will be performed using IMWG PET criteria, where a negative PET is described as disappearance of every area of increased tracer uptake found at disease sites on the baseline ¹⁸F-FDG PET/CT, or a preceding ¹⁸F-FDG PET/CT, or decrease to less than that seen in mediastinal blood SUV.⁴

However, other criteria including IMPETUS and IMAJEM trial criteria will also be applied as exploratory analyses to determine if a better reading scheme can be established with respect to accuracy in the prediction of patient outcome.^{29,45}

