6.1 Response Considerations

The International Myeloma Working Group (IMWG) uniform response criteria will be adapted to assess response to therapy in this trial.^{4,44} Since patients are entering the study at end of defined duration of therapy, and baseline disease parameters may not be known, we will limit the assessments to categories that are independent of baseline values (i.e., MRD negative, sCR, CR, and VGPR as defined below).

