6.2.1.1 Sustained MRD Negative

MRD negativity in the marrow (NGF or NGS, or both) and by imaging as defined below, confirmed minimum of 1 year apart. Subsequent evaluations can be used to further specify the duration of negativity (e.g., MRD-negative at 5 years)

6.2.1.2	Flow MRD Negative Absence of phenotypically aberrant clonal plasma cells by NGF on bone marrow aspirates using the EuroFlow standard operation procedure for MRD detection in multiple myeloma (or validated equivalent method) with a minimum sensitivity of 1 in 10^5 nucleated cells or higher
6.2.1.3	Sequencing MRD Negative Absence of clonal plasma cells by NGS on bone marrow aspirates in which presence of a clone is defined as less than two identical sequencing reads obtained after DNA sequencing of bone marrow aspirates using the ClonoSEQ platform (or validated equivalent method) with a minimum sensitivity of 1 in 10^5 nucleated cells or higher
6.2.1.4	Imaging Plus MRD Negative MRD negativity as defined by NGF or NGS plus disappearance of every area of increased tracer uptake found at baseline or a preceding PET/CT or decrease to less than mediastinal blood pool SUV or decrease to less than that of surrounding normal tissue
6.2.2	Standard IMWG Response Category
6.2.2.1	Stringent Complete Response (sCR) CR as defined below plus all of the following: 
• Normal serum FLC ratio at two consecutive times and• Absence of clonal cells in bone marrow by immunohistochemistry or 2- to 4- color flow cytometry.^a• Presence/absence of clonal cells is based upon the κ/λ ratio. An abnormal κ/λ ratio by immunohistochemistry requires a minimum of 100 plasma cells for analysis. An abnormal ratio reflecting presence of an abnormal clone is κ/λ ratio of 4:1 or 1:2.
6.2.2.2	Complete Response (CR) Patients who have complete disappearance of an M-protein and no evidence of myeloma in the bone marrow are considered to have complete response. To be considered CR, patients must meet all of the following criteria: 
• Negative immunofixation on the serum and urine• Disappearance of any soft tissue plasmacytomas• $\leq 5\%$ plasma cells in bone marrow• If the only measurable disease is FLC, a normal FLC ratio of 0.26-1.65
6.2.2.3	Very Good Partial Response (VGPR) 
• Serum M-protein detectable by immunofixation but not quantifiable on electrophoresis AND

- Urine M-protein < 100 mg/24 hours

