Rev. Add3 7. Serum and urine immunofixation and serum FLC only need to be repeated to confirm sCR or CR.

Rev. Add3 8. Within 8 weeks of pre-registration Step 0.

Rev. Add3 9. Follow-up post-treatment till progression. After progression, follow for survival for a maximum of 10 years. Every 3 months if patient is < 2 years from randomization, every 6 months if patient is 2-5 years from randomization, every 12 months if patient is 5 years or more from randomization. No specific requirements if patient is more than 10 years from randomization.

10. All specimens must be entered and tracked via the online ECOG-ACRIN Sample Tracking System (STS). See Section [10.3](#)

11. End of cycles 12, 24, 36 and 60 (\pm 6 weeks) only

12. End of cycles 12 and 24 (\pm 6 weeks) only

13. Institutions must upload immunofixation test results via Medidata Rave to determine eligibility status for Step 1 randomization.

14. Please refer to Section [8.2.8](#) and www.celgeneriskmanagement.com for information about the Revlimid REMS® program.

15. As clinically indicated.

Rev. Add3 16. Height is only required at baseline (prior to randomization) and does not need to be repeated.

8. Drug Formulation and Procurement

Investigator Brochure Availability

The current versions of the IBs for the agents will be accessible to site investigators and research staff through the PMB OAOP application. Access to OAOP requires the establishment of a CTEP IAM account and the maintenance of an “active” account status, a “current” password and active person registration status. Questions about IB access may be directed to the PMB IB Coordinator via email.

Useful Links and Contacts

- CTEP Forms, Templates, Documents: <http://ctep.cancer.gov/forms/>
- NCI CTEP Investigator Registration: [contact]
- PMB policies and guidelines:
http://ctep.cancer.gov/branches/pmb/agent_management.htm
- PMB Online Agent Order Processing (OAOP) application:
<https://ctepcore.nci.nih.gov/OAOP>
- CTEP Identity and Access Management (IAM) account:
<https://ctepcore.nci.nih.gov/iam/>
- CTEP IAM account help: [contact]
- IB Coordinator: [contact]
- PMB email: [contact]
- PMB phone and hours of service: [contact] Monday through Friday between 8:30 am and 4:30 pm (ET)

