Qualitative criteria are described in protocol Section [12.1.2](#). These criteria will be used to dichotomize the baseline ¹⁸F-FDG PET/CT scans as either negative or positive, where analyses using the IMPETUS and IMAJEM criteria are considered exploratory. The association between a positive/abnormal baseline ¹⁸F-FDG PET/CT scan and PFS will be assessed through Kaplan-Meier curves with the log-rank test. An adjusted analysis will also be conducted using a Cox regression model, with adjustment for potential confounders, including patient age and the randomization stratification factors. In addition, we will formally test whether this association differs by study arm through a statistical interaction term between ¹⁸F-FDG PET/CT positivity and study arm. If this interaction is not significant at the 0.5 level, then a single overall hazard ratio will be estimated for the entire study cohort. It is anticipated that between 50-70% of patients will have a positive ¹⁸F-FDG PET/CT scan at baseline. Assuming 60% of patients have a positive ¹⁸F-FDG PET/CT scan at baseline, the proposed sample size of 510 patients (459 evaluable) yields 87% power at a type I error rate of 0.05 to detect a difference in median PFS between ¹⁸F-FDG PET/CT-positive and ¹⁸F-FDG PET/CT-negative patients as low as 7 months (19 vs. 26 months, respectively, assuming 3 years of accrual time and 4.5 years of patient follow-up; PASS 16).

Similar analyses will be conducted for the OS outcome. OS will be defined as the time from randomization until death or the date last known alive.

The ¹⁸F-FDG PET/CT images will be collected centrally and archived for future research analysis. All data and results will be anonymized.

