12.1.3.2 Secondary imaging aims

[2] To compare overall survival (OS) with the addition of ixazomib to lenalidomide among baseline ¹⁸F-FDG PET/CT-positive and ¹⁸F-FDG PET/CT-negative subgroups.

This secondary imaging aim consists of a subgroup analysis of the trial primary endpoint, and will assess for heterogeneity of treatment effect by baseline ¹⁸F-FDG PET/CT status. If such heterogeneity is detected, this

would suggest that the effectiveness of ixazomib treatment could be increased by targeting patients with the appropriate baseline ^{18}F -FDG PET/CT status.⁵⁵

Heterogeneity of treatment effect will be assessed at full information, using a two-sided statistical test for interaction between study arm (ixazomib/lenalidomide vs. placebo/lenalidomide) and baseline ^{18}F -FDG PET/CT status (positive/abnormal vs. negative) in a Cox regression model.^{56,57} If the statistical test for interaction is not significant at the 0.05 level, we will conclude that there is not sufficient evidence for heterogeneity of treatment effect; if the statistical test for interaction is significant, estimated treatment hazard ratios for OS (ixazomib arm vs. placebo arm) will be reported separately for baseline ^{18}F -FDG PET/CT-positive and ^{18}F -FDG PET/CT-negative subgroups, along with the corresponding 95% confidence intervals. OS will be defined as the time from randomization until death or the date last known alive.

We anticipate between 50-70% of patients will have a positive ^{18}F -FDG PET/CT scan at baseline. Sensitivity of the findings will be examined by adjusting the Cox model for patient age and the randomization stratification factors.

[3] To compare the change in quantitative ^{18}F -FDG PET/CT parameters over time with the addition of ixazomib to lenalidomide.

This secondary imaging aim consists of comparing the change in ^{18}F -FDG PET/CT parameters over time across study arms and seeks to address the question of whether adding ixazomib to lenalidomide results in sharper decreases in ^{18}F -FDG uptake (as measured by ^{18}F -FDG PET/CT) compared to lenalidomide plus placebo, thus giving evidence of greater disease control.

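### The rule for a negative PET compares a scan with an earlier one, yet it is used to classify the baseline scan, and OS hazard ratios by PET group are promised only after a significant interaction test

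*Combined protocol and SAP*

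**What the plan says.** **The rule.** Section 12.1.2 gives the primary reading in three limbs joined by *or*. The first is "a negative PET is described as disappearance of every area of increased tracer uptake found at disease sites on the baseline" PET/CT. The second is the same test against a preceding PET/CT. The third is "or decrease to less than that seen in mediastinal blood SUV".

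**Where it is used.** Section 12.1.3.1 says of the qualitative criteria: "These criteria will be used to dichotomize the baseline" scans as negative or positive. Section 12.1.3.2 uses the resulting status in the treatment-by-PET interaction for OS.

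**Which scan is the baseline.** Section 12.1.1 places it "Prior to initiation of randomized study mandated therapy [referred to as the baseline scan", and the footnote to the schedule in 7.1 allows it "Within 8 weeks of pre-registration Step 0". The later scheduled scans follow cycles 12 and 24.

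**A second wording.** Section 6.2.1.4 states the imaging rule with an extra limb: "decrease to less than mediastinal blood pool SUV or decrease to less than that of surrounding normal tissue".

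**Reporting.** Objective 2.5.2 is to compare OS between treatments in the PET-positive and PET-negative subgroups. Section 12.1.3.2 says that "if the statistical test for interaction is significant, estimated treatment hazard ratios for OS (ixazomib arm vs. placebo arm) will be reported separately" for the two groups. If the test is not significant at 0.05, the plan states only that evidence of heterogeneity is insufficient.

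**The concern.** The rule describes response over time, but the qualitative half of imaging aim 1 and all of aim 2 need the PET state at one moment, about a year into maintenance. Patients enter after induction, transplant and maintenance, and the trial neither schedules nor collects a diagnostic or pre-transplant PET. The plan recognises this kind of gap elsewhere. Section 6.1 restricts the response categories because "baseline disease parameters may not be known", and section 1.2 prefers flow cytometry to sequencing because it needs no baseline specimen. The PET rule was not adapted in the same way.

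At stake is whether the positive/negative split is fixed in advance. If it is not, central readers must choose a convention, and that choice determines who falls in each group for the PFS, OS and interaction analyses.

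The reporting rule is a separate matter. It makes the estimates named in objective 2.5.2 depend on a test with limited power.

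**Working it through.** **1. The limbs of 12.1.2 applied to the baseline scan**

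- Limb 1 (against baseline): the scan is compared with itself. It can be met only trivially, when there is no uptake.
- Limb 2 (against a preceding scan): sections 1.5.3, 7.1 and 12.1.1 schedule baseline, cycle 12 and cycle 24 scans. Section 1.5.3 adds scans for MRD confirmation. None is an earlier scan collected for the baseline read.
- Limb 3 (blood pool): the reference lies within the same scan, so it can serve as a threshold. As written it is a decrease, and nothing says that it alone governs baseline.

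For a patient with no earlier scan, the possible readings are:

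| Disease-site uptake at baseline | 12.1.2, limb 3 as a threshold | 12.1.2, decrease must be shown | 6.2.1.4, limbs as thresholds |
|---|---|---|---|
| None | negative | negative | negative |
| Present, below blood pool | negative | not shown | negative |
| At or above blood pool, below surrounding normal tissue | positive | positive | negative |
| At or above both | positive | positive | positive |

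The middle two rows depend on the convention chosen. The documents do not say how many patients fall there.

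**2. The stated 87% power (12.1.3.1)**

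Inputs from 12.1.3.1: 459 evaluable, 60% positive, median PFS 19 vs 26 months, 3 years of accrual, 4.5 years of follow-up, alpha 0.05 (taken as two-sided). Follow-up is read as starting when accrual ends.

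- Hazards: ln2/19 = 0.03648 and ln2/26 = 0.02666 per month; HR = 26/19 = 1.368.
- Event probability = 1 − (e^(−54λ) − e^(−90λ))/(36λ), which gives 0.922 and 0.848.
- Events: 275.4 × 0.922 + 183.6 × 0.848 ≈ 410.
- Schoenfeld: √(409.6 × 0.6 × 0.4) × ln 1.368 − 1.96 = 1.15, power 0.875. An exponential log-hazard test gives 0.869.

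The 87% reproduces. If 4.5 years is instead total study time, the same formula gives 0.767, so the first reading is the one that matches.

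**3. The quantitative half (12.1.3.1)**

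√(459 × 0.6 × (1 − 0.4)) × ln 1.25 − 1.96 = 0.908, power 0.818 against the stated 82%. SUVmax, SUVpeak, MTV and TLG enter as continuous covariates, so the split plays no part.

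**4. Interaction power for OS by PET status (12.1.3.2)**

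The 179 deaths at full information come from 9.3.1. Assumptions: 90% of deaths occur in patients with a readable scan, deaths divide 60:40 by PET status, and they divide about equally between arms within each group.

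- Deaths: 179 × 0.9 ≈ 161, that is about 97 and 64.
- SE of the log ratio of hazard ratios = √(4/97 + 4/64) = 0.322.
- Two-fold ratio: 0.693/0.322 − 1.96 = 0.19, power about 58%.
- 1.5-fold ratio: 0.405/0.322 − 1.96 = −0.70, power about 24%.
- Ratio detectable with 80% power: exp(2.80 × 0.322) ≈ 2.5, and about 2.4 to 2.6 over the plan's 50–70% positive range.

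**5. Illustration of misclassification (error rates assumed, not in the documents)**

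Simulated log-rank power on the basis of step 2, with 3,000 runs and equal error each way:

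| Error each way | Power |
|---|---|
| 0% | 0.87 |
| 5% | 0.79 |
| 10% | 0.69 |
| 20% | 0.44 |

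Analytic check at 10%: the truly positive share is 0.54/0.58 = 0.931 among those labelled positive and 0.06/0.42 = 0.143 among those labelled negative, a contrast of 0.788. With z = 3.086 for 87% power, 3.086 × 0.788 − 1.96 = 0.47, power 0.68.

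**The case against.** The best defence is that the blood-pool limb is an alternative, not an addition, and its reference is within the scan. A central reader could apply it to every baseline scan. This stands: a reader might infer that the rule cannot be used at all without an earlier scan, and that is too strong. What remains is that the limb is worded as a decrease and is not named as the baseline criterion.

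A reader might also infer that some patients will be judged against old scans and others against none. The documents do not support that. Section 12.1.3 bases the imaging aims on central review of the acquired scans, and nothing says that older local scans reach the readers. Nor should limb 2 be taken to mean that the plan accepts new lesions as negative: sections 6.2.1 and 6.2.2.4 count new bone lesions against MRD negativity or as progression, although those are response rules and not PET reading rules.

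On reporting, holding back subgroup estimates until an interaction test is significant is a recognised guard against over-reading them. That guard belongs on the claim of heterogeneity. It is a poor reason not to commit to estimates that are themselves the stated objective.

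**Conclusion.** The point holds as a gap in definition plus a separate gap in reporting. The primary PET rule is not written for the scan it must classify, and 12.1.2 and 6.2.1.4 differ. This affects the qualitative half of imaging aim 1 and the OS-by-PET aim. It would be wrong to say that the whole primary imaging aim rests on the split, because the quantitative half does not use it. The trial's OS and PFS comparisons between arms are untouched.

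No stated power figure is shown to be wrong. The losses to 0.79, 0.69 and 0.44 show what misclassification of an assumed size would do. They do not estimate what this wording will cause.

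Under the assumptions in step 4, the plan would not commit to the subgroup hazard ratios in about 42% of trials with a true two-fold ratio and about 76% with a 1.5-fold ratio. With no heterogeneity the figure is about 95%, from the 0.05 level of the test. The text does not forbid reporting them in those cases; it simply makes no commitment to do so.

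**What to change.** 1. In 12.1.2, add a single-scan rule for the central baseline read: negative if there is no disease-site uptake, or if all such uptake is less than mediastinal blood pool SUV; otherwise positive. This uses the plan's own threshold and keeps its less-than boundary.
2. Keep the disappearance rule for the year 1 and year 2 scans.
3. Reconcile 12.1.2 with 6.2.1.4 on the surrounding-normal-tissue limb, and say whether it applies at baseline.
4. In 12.1.3.2, report the treatment hazard ratio for OS with its 95% CI in both PET groups whatever the interaction p-value. The interaction test continues to govern any claim of heterogeneity.

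The cost is wording in the protocol and in the instructions for central reading. No extra scans or patients are needed. The baseline rule should be fixed before central reading and before anyone sees outcome by PET status.
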